The primary effectiveness endpoint will be evaluated using the Win Ratio method of analysis for a hierarchical composite endpoint based on the Finkelstein-Schoenfeld test (Finkelstein and Schoenfeld, 1999; Pocock, et al., 2012) with three components: a) fatal bleeding events occurring within 48hrs of the index procedure, b) moderate, severe, or massive bleeding based on the Universal Definition of Perioperative Bleeding in Cardiac Surgery (UDPB) ≥ 2 classification, and c) 24-hour chest tube drainage (volume, mL). The Win Ratio assigns “wins”, “losses”, or “ties” between randomized groups in a serial fashion across all components of the composite endpoint adhering to the declared hierarchical order from higher to lower clinical importance.[14] [15] A ratio of “wins” greater than 1.0 favors the treatment arm; when the lower bound of a 95% confidence interval (CI) around the ratio exceeds 1.0, the treatment is shown to be statistically superior to control at alpha = 0.05. The primary effectiveness analysis will be performed in the overall study population comprised of both apixaban and rivaroxaban patients to evaluate the difference between the SOC (control) arm and the DrugSorb-ATR (investigational) arm.

The key secondary effectiveness endpoints are the pre-CPB vs. post-CPB change in drug levels (apixaban and/or rivaroxaban) measured by liquid chromatography/tandem mass spectrometry (LC/MS-MS) [drug removal endpoint]. Change in each subject's blood concentration of apixaban or rivaroxaban from immediately *before* to immediately *after* CPB will be collected and analyzed by a central core laboratory. Drug removal will be analyzed for apixaban and rivaroxaban independently.

Change from baseline in blood concentration of apixaban or rivaroxaban is defined as:

$$\frac{\text{pre-CPB [apixaban]}_{\text{blood}} - \text{post-CPB [apixaban]}_{\text{blood}}}{\text{pre-CPB [apixaban]}_{\text{blood}}} * 100\%$$

or

$$\frac{\text{pre-CPB [rivaroxaban]}_{\text{blood}} - \text{post-CPB [rivaroxaban]}_{\text{blood}}}{\text{pre-CPB [rivaroxaban]}_{\text{blood}}} * 100\%$$

Based on existing benchtop evidence, a conservative estimate of 40% reduction in blood concentration of DOAC between pre- and post- DrugSorb-ATR removal is expected, with a standard deviation of 40%, in the treatment arm. Minimal change is expected in the control arm. A two-sample t-test will be used to evaluate the difference between treatment arms.

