A planned interim analysis will be performed after 70% of study subjects have completed the study, to allow for early stopping for overwhelming efficacy according to a pre-specified boundary.

Subgroup Analyses

Subgroup analyses will be conducted to investigate efficacy of treatment. These include analyses by DOAC drug type, site, and type of planned cardiothoracic surgery.

Analysis Populations

Enrolled subjects include all subjects who provide informed assent/consent. Enrolled subjects who do not meet criteria for study eligibility are screening failures and will exit the study.

The Intent-to-Treat (ITT) Population will include all enrolled (assented/consented) subjects who are randomized. The modified Intent-to-Treat (mITT) Population will include all randomized subjects who undergo the index surgical procedure **and** receive a study device (whether DrugSorb-ATR or *sham*). The primary analyses of the trial will be performed on the mITT Population. Baseline demographic and clinical variables will be summarized for each of the treatment groups for the ITT and mITT populations. So long as the ITT and mITT populations are not identical, the ITT patients who do not fall within the mITT population will be presented in a listing, including the reasons for why they did not receive a study device. The Per Protocol (PP) Population will include all mITT subjects who have no major protocol violations. Analysis of the primary efficacy endpoint will be performed in the PP population as a sensitivity analysis.

The Safety Analysis Population will include all enrolled subjects who are treated or attempted treatment with a study device. “Attempted treatment” refers to any subject(s) who initiate treatment with a study device (whether DrugSorb-ATR or *sham*) during the index procedure but experience early discontinuation.

Safety Analysis

All AEs occurring after the start of the CPB procedure will be listed and summarized using descriptive methodology. The incidence of AEs will be presented by severity and by relationship to the investigational device (DrugSorb-ATR or *sham*) as determined by the Investigator (or designee). Each AE will be coded using the Medical Dictionary for Regulatory Activities®. Observed values for clinical laboratory test data and vital signs, along with change from baseline results, will be summarized by collection time point. A summary of clinically notable values will be provided.

Safety oversight committees:

DSMB:

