11. STATISTICAL CONSIDERATIONS

General statistical considerations: descriptive summaries will be presented using mean with standard deviation (SD), median, minimum and maximum for continuous variables and as count and percent of subjects for categorical variables. Inferential statistical tests will be two-sided and use alpha (α) of 0.05 as a critical value, unless noted otherwise. Statistical analysis will be carried out using SAS Version 9.4 or later and/or R software language.

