11.3. Effectiveness Analysis

The primary effectiveness endpoint will be evaluated using the Win Ratio method of analysis for a

hierarchical composite endpoint based on the Finkelstein-Schoenfeld test (Finkelstein and Schoenfeld, 1999; Pocock, et al., 2012) with three components ranked in order of clinical importance: a) fatal bleeding events occurring within 48hrs post-index procedure, b) moderate, severe, or massive perioperative bleeding events according to the Universal Definition of Perioperative Bleeding in Cardiac Surgery (UDPB) classification ≥ 2 , and c) 24-hour chest tube drainage (mL) following surgery. [14] [15] The Win Ratio assigns “wins”, “losses”, or “ties” in sequential comparisons between treatment and control arm subjects according to the hierarchical order of the components of the primary composite endpoint.

There are two key advantages to the Win Ratio method of analysis. First, the hierarchical assessment of the individual components of the composite endpoint according to their clinical significance. Second, the opportunity for different types of components, such as categorical versus continuous, to all be included thereby capturing all available information from each component to increase statistical power.[15] A Win Ratio along with a two-sided 95% CI will be estimated, and a Win Ratio greater than 1.0 favors the treatment arm; when the lower bound of a two-sided 95% confidence interval (CI) around the ratio exceeds 1.0, the treatment is shown to be statistically superior to control at alpha = 0.05.[16] The primary effectiveness analysis will use a combined DOAC population to evaluate the difference between the SOC (control) arm and the DrugSorb-ATR (investigational) arm. The key secondary effectiveness endpoints are drug removal endpoints, namely the percent change in pre-CPB vs. post-CPB apixaban and rivaroxaban levels as measured by liquid chromatography/tandem mass spectrometry (LC/MS-MS). Blood samples for drug removal analyses will be collected and analyzed by a central core laboratory.

Change from baseline in blood concentration of apixaban or rivaroxaban is defined as:

$$\frac{\text{pre-CPB [apixaban]blood} - \text{post-CPB [apixaban]blood}}{\text{pre-CPB [apixaban]blood}} * 100\%$$

and

$$\frac{\text{pre-CPB [rivaroxaban]blood} - \text{post-CPB [rivaroxaban]blood}}{\text{pre-CPB [rivaroxaban]blood}} * 100\%$$

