Type I error (alpha, α) will be preserved from inflation due to multiplicity across the primary effectiveness, key secondary, and secondary endpoints via a hierarchical closed testing step-down approach. Only if preceding endpoints are declared statistically significant at the alpha 0.05 level, can further endpoints also be declared significant. The order of hierarchical testing will follow the order of primary, key secondary, and secondary endpoints as listed in the paragraph above, namely: the primary endpoint will be tested first, followed by the first key secondary endpoint (percent change in pre-CPB vs. post-CPB blood apixaban levels), followed by the second key secondary endpoint (percent change in pre-CPB vs. post-CPB blood rivaroxaban levels), followed by the first secondary endpoint (24-hour CTD), second secondary endpoint (platelet transfusions), and lastly the third secondary endpoint (pRBC transfusions).

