11.6. Interim Analysis

An interim analysis with unblinded efficacy assessment is planned once 70% of evaluable subjects (n=40 per group) have completed the primary effectiveness assessment, including follow-up period. All data for the interim primary effectiveness endpoint will be fully adjudicated by the CEC prior to analysis. The interim evaluation will be performed with possible early stopping for efficacy on the basis of a Lan-DeMets O'Brian-Fleming spending function, which generates group-sequential boundaries that resemble O'Brian-Fleming boundaries, with experiment-wise error preserved at 0.05. [44, 45] Based on simulation results, a Win Ratio Z-value boundary of 2.44 would need to be crossed, corresponding to a two-sided p-value of 0.0148. Should the interim efficacy boundary not be crossed, a total alpha of 0.0148 would be spent at the interim, plus 0.0352 spent at the final analysis. In this case, at the final analysis a Win Ratio Z-value of 2.00 would need to be crossed, corresponding to a p-value of 0.0456, to declare a statistically significant Win Ratio result favoring the treatment arm. The estimated probability of stopping due to efficacy at the interim is >88.1%.

To maintain study blinding, the interim analysis will be conducted by an independent unblinded statistician separate from the day-to-day operational team with appropriate experience. Enrollment will not be paused during the interim analysis. Interim analysis results will be shared only with the DSMB, which will make a decision to either stop the study early due to overwhelming efficacy or continue until the final analysis. The FDA will be immediately notified of any decision by the DSMB to halt or terminate the study early. Should the study stop early, a final analysis will also take place that will include any additional subjects who were treated and followed-up during the conduct of the interim analysis.

To prevent potential operational bias resulting from the interim analysis, the clinical personnel at sites may not be informed of the interim results. Details on the interim analysis methodology will be provided in the SAP.

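### The 95% CI success rule in the Synopsis and Section 11.3 conflicts with the Z = 2.00 boundary that Section 11.6 sets for the final analysis, and the plan does not say which prevails

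*Combined protocol and SAP*

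**What the plan says.** **Section 11.3, Effectiveness Analysis.** The primary criterion is that "when the lower bound of a two-sided 95% confidence interval (CI) around the ratio exceeds 1.0, the treatment is shown to be statistically superior", at alpha 0.05. The interim look is not mentioned and Section 11.6 is not cited.

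**Synopsis, Statistical methods.** The same rule appears: "when the lower bound of a 95% confidence interval (CI) around the ratio exceeds 1.0, the treatment is shown to be statistically superior". The Synopsis mentions a boundary only for the interim look, whose purpose is "to allow for early stopping for overwhelming efficacy according to a pre-specified boundary".

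**Section 11.3, multiplicity paragraph.** The step-down gate reads: "Only if preceding endpoints are declared statistically significant at the alpha 0.05 level, can further endpoints also be declared significant". Five tests stand behind the primary: apixaban change, rivaroxaban change, 24-hour chest tube drainage, platelet transfusions and pRBC transfusions.

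**Section 11.6, Interim Analysis.** With Lan-DeMets O'Brien-Fleming spending and an experiment-wise error of 0.05, the interim boundary is Z = 2.44 (p = 0.0148). If it is not crossed, "at the final analysis a Win Ratio Z-value of 2.00 would need to be crossed, corresponding to a p-value of 0.0456", and this is needed "to declare a statistically significant Win Ratio result favoring the treatment arm".

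**Section 11, opening paragraph.** "Inferential statistical tests will be two-sided and use alpha (α) of 0.05 as a critical value, unless noted otherwise".

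**The concern.** The plan gives two thresholds for one decision. Excluding 1.0 from a two-sided 95% CI corresponds to |Z| > 1.96, that is p < 0.05. Section 11.6 asks for Z = 2.00, p = 0.0456. A final p-value between 0.0456 and 0.05 is a success by Section 11.3 and the Synopsis and a failure by Section 11.6.

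Nothing in the text settles the order of precedence outright. The general exception clause at the head of Section 11 points towards 11.6 but does not name it, while Section 11.3 states its own specific rule for this endpoint. A reader looking for the boundaries is not helped by Section 1.5 either: it refers to Section 11.4, which in the current text is Subgroup Analysis.

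At stake are the pivotal claim, access to the secondary hierarchy, and the 0.05 experiment-wise error that Section 11.6 promises. A result inside the band would have to be resolved after unblinding, when either choice could be challenged.

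**Working it through.** **Inputs.** Overall two-sided alpha 0.05; interim at 70% of evaluable subjects, n = 40 per group; boundaries 2.44 and 2.00 (all Section 11.6). 57 evaluable per arm, and the Table 3 scenario with equal event rates for the two drugs: fatal bleeding 3.00% in each arm, UDPB class ≥2 24.30% vs 40.50%, chest tube drainage 480 vs 800 mL with SD 253 (Section 11.1).

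**1. Reproduce Section 11.6.** The O'Brien-Fleming-type spending function, applied with 0.025 per side at t = 0.70, gives

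α(t) = 4 × [1 − Φ(z₀.₉₈₇₅/√t)] = 4 × [1 − Φ(2.2414/√0.70)] = 0.01477,

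so Z₁ = 2.438. The alpha left is 0.05 − 0.0148 = 0.0352. Solving P(|Z₁| ≥ c₁ or |Z₂| ≥ c₂) = 0.05 for a bivariate normal with correlation √0.70 gives c₂ = 2.000, nominal p = 0.0455. The plan prints 2.44, 0.0148, 0.0352, 2.00 and 0.0456, so its figures reproduce to rounding.

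**2. Overall two-sided alpha under each final rule (t = 0.70).**

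| Interim boundary | Final boundary | Overall alpha |
|---|---|---|
| 2.44 | 2.00 (Section 11.6) | 0.04995 |
| 2.44 | 1.96 (95% CI rule) | 0.05411 |

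The excess is 0.05411 − 0.04995 = 0.00416, or 0.42 percentage points. With the plan's own sample sizes, the second row is 0.0542 at t = 39/56 (Table 3) and 0.0541 at t = 40/57 (Section 11.6). If the 95% CI rule were also applied at the interim, overall alpha would be 0.0756. That contradicts the explicit text of Section 11.6 and is only an outer limit.

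**3. Chance of a disputed result.** Under the null, P(|Z₁| ≤ 2.44 and 1.96 < |Z₂| ≤ 2.00) = 0.00416. Under the plan's assumptions it was estimated from 6,000 simulated trials with 40 and then 57 per arm, independent components, and normal drainage truncated at 0. The frequency was 0.0005, that is 3 trials (exact 95% interval about 0.01% to 0.15%).

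**4. Power.** In the same simulation, overall rejection was 99.57% with 2.44/2.00 and 99.62% with 2.44/1.96. As a check on the model, a separate run of 4,000 Finkelstein-Schoenfeld tests gave 91.5% at n = 39 with Z > 2.44 (Table 3: 91.3%) and 99.5% at n = 56 with Z > 2.00 (Table 3: 99.5%).

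**5. Matching CI levels.** Interim: 1 − 0.0148 = 98.52%. Final: 1 − 0.0456 = 95.44%.

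**The case against.** The best reply is that the plan nearly answers the question itself. Section 11 sets 0.05 as a default with exceptions, and Section 11.6 reads as such an exception. It is the only passage that addresses the final analysis after an interim look, it gives a number, and it promises overall control at 0.05. Section 11.3 and the Synopsis never say that their rule is for the final analysis; they could be read as a general account of how a win ratio interval is interpreted. This stands to a degree: the alpha adjustment is not missing, and Section 11.6 is the natural reading. It does not repair a fixed 95% level attached to an explicit statement of superiority.

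A second reply is that alpha of 0.05 is sometimes used as the trial-wise level. The power statements in the Synopsis and Section 11.1 quote 0.05 while assuming the interim, so the gate in Section 11.3 could mean the same. That is fair, and it makes the gate weaker evidence of conflict than the CI rule. The 95% interval cannot be read that way.

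Third, equating the CI rule with |Z| > 1.96 assumes that the interval and the test use the same statistic, and the plan gives no CI method. With different variance estimates the edges of the band would move, but an interval at 95% would still not match a boundary of p = 0.0456.

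Finally, the effect is very small. That is true, and it limits the weight of the point. It does not justify leaving two rules for the primary verdict.

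**Conclusion.** The concern holds. As written, the Synopsis and Section 11.3 state a final threshold that is too lenient for a design with one efficacy look, and it contradicts Section 11.6. The Section 11.6 boundaries are right and keep overall two-sided alpha at 5.00%; the 95% CI rule at the final analysis would make it 5.41%. The disputed band carries 0.42% probability under the null and about 0.05% under the plan's effect assumptions. These figures rest on a jointly normal test statistic with correlation √t, on the same statistic underlying test and interval and, for the 0.05% and the power figures, on independent components. This is a wording defect with an inferable answer. It should be corrected before any unblinded look because it governs the primary claim and the tests behind it.

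**What to change.** In the Synopsis and Section 11.3, replace the 95% CI criterion with a rule such as:

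> Superiority is declared only if the Win Ratio Z-value crosses the Section 11.6 boundary: 2.44 at the interim, or 2.00 at the final analysis if the interim boundary was not crossed.

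This also covers early stopping, since superiority has then already been declared at the interim.

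- Report the win ratio with a 98.52% CI at the interim and a 95.44% CI at the final analysis. Label any 95% CI as descriptive.
- State that the Win Ratio Z-value named in Section 11.6 decides, and that the test and the CI use the same statistic.
- In the multiplicity paragraph, for the primary endpoint only, replace significance at the 0.05 level with crossing its Section 11.6 boundary. This leaves the level for the secondary endpoints as it is.

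The cost is wording. The final threshold becomes slightly stricter than Section 11.3 now states (0.0456 instead of 0.05) and is unchanged from Section 11.6. Simulated power differs by 0.05 percentage points (99.62% − 99.57%, a difference of 3 trials in 6,000), so no change in sample size is needed.

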Additional powered secondary endpoints include 24-hour CTD (volume [mL]), total platelet transfusions (volume [mL] and units), and total PRBC transfusions (volume [mL] and units) during the index hospitalization. Twenty-four-hour CTD (mL) will be assessed via two-sample t-test for mean difference. The transfusion endpoints will all be analyzed using two-sample t-tests for mean differences, and Fisher-Freeman-Halton exact tests for units. In the event the assumptions for a two-sample t-test are not met in any of the above, a nonparametric test such as a Mann-Whitney test will be employed, with median and range values provided in the output. An additional analysis of 24-hour CTD will compare the frequency of subjects falling into volume categories (i.e., <500 mL, 500 to <750 mL, 750 to <1000 mL, 1000 to <1250 mL, 1250 to <1500 mL, and ≥ 1500 mL), and will use a Fisher-Freeman-Halton exact test to compare treatment groups. Other secondary endpoints include the remaining Win Ratio component parts: proportions of fatal perioperative bleeding events will be assessed via Fisher's exact test; and proportions of UDPB events (by category) will be assessed via a Fisher-Freeman-Halton exact test. The secondary endpoint of surgical re-exploration for bleeding will take into account time to re-exploration.

Sample Size

Approximately 120 subjects will be randomized in a 1:1 ratio to the treatment and control arms. Assuming a 5% dropout rate, at total of 114 subjects (57 per arm) are expected to be evaluable for effectiveness and safety. Sample size is based on assumed response rates for the primary effectiveness endpoint, and power can be calculated via an iterative simulation process with programming code available in an appendix to Redfors et al. (2019).[16] With a Finkelstein-Schoenfeld test, total of 57 subjects per arm ensures power of $>99.2\%$, using a two-sided alpha (α) of 0.05, and assuming an interim analysis for efficacy at 70% completion. Power for each of the key secondary endpoints is estimated at 96.3%, and for 24-hour chest tube drainage (mL), $>99.9\%$, based on a two-sample t-test assuming equal variance and a two-sided alpha of 0.05.

Similarly, although assuming unequal variances, power for comparisons of platelet transfusions (volume [mL]) and PRBC transfusions (volume [mL]), is estimated at 98.0% and 96.7%, respectively.

Interim Analysis

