11.1. Statistical Power and Sample Size Determination

Overall study sample size is designed to provide adequate power for the primary effectiveness endpoint, at both the interim and final analysis, the key secondary endpoints, and selected secondary endpoints.

As noted above ([Section 6.2](#)), to maintain the balance between sites in terms of numbers of subjects randomized, study sites will be capped at randomizing a maximum of 15% of the overall study sample (i.e., 18 subjects). For sites with a total enrollment consisting of only one type of DOAC drug as per chance, the randomization cap will be replaced by a maximum of 10% of the overall study sample

(i.e., 12 subjects).

The null hypothesis for the primary composite endpoint is represented by:

H_0 : The distributions of the components are the same in the two treatment groups

The alternative hypothesis for the primary composite endpoint is represented by:

H_A : For at least one component, the distribution is different between the treatment groups

The null hypothesis for the first key secondary endpoint is represented by:

$H_0: \pi_{DS} = \pi_{SOC}$

The alternative hypothesis for the first key secondary endpoint is represented by:

$H_A: \pi_{DS} \neq \pi_{SOC}$

where $\pi_{1,DS}$ and $\pi_{1,SOC}$ are the pre-CPB vs. post-CPB mean percent changes in blood apixaban levels with DrugSorb-ATR (DS) and Control (SOC), respectively. The second key secondary endpoint null and alternative hypotheses take the same form as the first key secondary endpoint but substituting rivaroxaban for apixaban.

The null hypothesis for the first secondary endpoint is represented by:

$H_0: \pi_{DS} = \pi_{SOC}$

The alternative hypothesis for the first secondary endpoint is represented by:

$H_A: \pi_{DS} \neq \pi_{SOC}$

where π_{DS} and π_{SOC} are the mean 24-hour CTD volumes with DrugSorb-ATR (DS) and Control (SOC), respectively. The following additional secondary endpoints, for which power is formally allocated (see below), take the same form of null and alternative hypotheses as above: platelet transfusions (mean number of units) and pRBC transfusions (mean number of units).

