Using a Finkelstein – Schoenfeld test, a total of 57 subjects per arm ensures power of >99.2% for the primary effectiveness endpoint at the final analysis, using a two-sided alpha (α) of 0.05, and assuming an interim analysis for efficacy at 70% completion. [15] Power for each of the key secondary endpoints is estimated at 96.3% assuming a $40\% \pm 40\%$ mean difference between treatment and control, where N=29 subjects receiving apixaban with N=29 corresponding controls along with parallel numbers of subjects receive rivaroxaban and corresponding control, based on a two-sample t-test assuming equal variance and a two-sided alpha of 0.05. For the 24-hour CTD secondary endpoint, assuming a treatment arm volume of 480 ± 253 mL and control arm volume of 800 ± 253 mL [12] [a discount is applied (see **Table 3** for details) to bring the Active arm up to ~40% reduction on the Control arm], power is similarly estimated at >99.9%. Power for comparisons of platelet transfusions between the treatment arm (0.32 ± 0.9 units) and control arm (1.6 ± 2.2 units) [43] is estimated at 98.0%, based on a two-sample t-test assuming unequal variance and a two-sided alpha of 0.05. Similarly, power for PRBC transfusions between the treatment arm (1.3 ± 2.1 units) and control arm (4.4 ± 5.7) [43] is estimated at 96.7%. Sample size and power for all secondary endpoints were calculated using PASS 2021 (NCSS, LLC. Kaysville, UT, USA, ncss.com/software/pass).

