Benchtop studies of drug removal by DrugSorb-ATR (data on file, CytoSorbents Corporation) demonstrate concentration and time dependent absolute drug removal, which are nearly identical for both apixaban and rivaroxaban. Based on these benchtop studies, a conservative estimate of 40% reduction in blood concentration of DOAC between pre- and post- DrugSorb-ATR removal is expected, with a standard deviation of 40%, in the treatment arm. Minimal change is expected in the control arm. A two-sample t-test will be used to evaluate the difference between treatment arms. Due to highly variable baseline drug levels in the study population, percent change from baseline will be analyzed as opposed to observed values.

Additional secondary endpoints include 24-hour CTD (volume [mL]), total platelet transfusions during the index hospitalization (volume [mL] and units), and total PRBC transfusions during the index hospitalization (volume [mL] and units). Twenty-four-hour CTD (mL) will be assessed via two-sample t-test for mean difference. In the event the assumptions for a two-sample t-test are not met, a nonparametric test such as a Mann-Whitney test will be employed, with median and range values provided in the output. An additional analysis of 24-hour CTD will compare the frequency of subjects falling into volume categories (i.e., <500 mL, 500 to <750 mL, 750 to <1000 mL, 1000 to <1250 mL, 1250 to <1500 mL, and ≥ 1500 mL), and will use a Fisher-Freeman-Halton exact test to compare treatment groups. The transfusion endpoints will all be analyzed using two-sample t-tests for mean differences, and Fisher-Freeman-Halton exact tests for units. In the event the assumptions for a two-sample t-test are not met, a nonparametric test such as a Mann-Whitney test will be employed, with

median and range values provided in the output. The remaining Win Ratio component parts will also be included as secondary endpoints: proportions of fatal perioperative bleeding events will be assessed via Fisher's exact test; and proportions of UDPB events (by category) will be assessed via a Fisher-Freeman-Halton exact test. All surgical re-exploration for excessive bleeding, including those events occurring beyond the timeframe captured within the UDPB component of the primary endpoint will be captured as a secondary endpoint. Time to re-exploration will be considered.

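### The Synopsis credits the platelet and PRBC power to mL although it was derived for units, and Section 11.3 does not name the measure and test that decide the last two confirmatory steps

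*Combined protocol and SAP*

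**What the plan says.** All references are to the combined protocol and SAP.

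- **Section 11.1, hypotheses.** The secondary endpoints with formally allocated power include "platelet transfusions (mean number of units) and pRBC transfusions (mean number of units").
- **Section 11.1, power.** "Power for comparisons of platelet transfusions between the treatment arm (0.32 ± 0.9 units) and control arm (1.6 ± 2.2 units") is put at 98.0%, "based on a two-sample t-test assuming unequal variance and a two-sided alpha of 0.05". The same paragraph puts "power for PRBC transfusions between the treatment arm (1.3 ± 2.1 units) and control arm (4.4 ± 5.7") at 96.7%.
- **Synopsis, Sample Size.** The same two figures are given to volume: "power for comparisons of platelet transfusions (volume [mL]) and PRBC transfusions (volume [mL]), is estimated at 98.0% and 96.7%, respectively".
- **Synopsis, Effectiveness Analysis.** Both measures are called powered: "Additional powered secondary endpoints include 24-hour CTD (volume [mL]), total platelet transfusions (volume [mL] and units), and total PRBC transfusions (volume [mL] and units").
- **Section 11.3, analysis.** Each transfusion endpoint is listed as volume and units. The tests are then assigned: "The transfusion endpoints will all be analyzed using two-sample t-tests for mean differences, and Fisher-Freeman-Halton exact tests for units". A nonparametric test, with Mann-Whitney as the example, replaces the t-test if its assumptions fail.
- **Section 11.3, testing sequence.** Platelet transfusions and then pRBC transfusions are the last two of six steps. Neither a measure nor a test is attached to them.

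**The concern.** Two things do not line up.

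First, the Synopsis and Section 11.1 attach the same power figures to different measures. A reader of the Synopsis would take transfused volume as the powered outcome.

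Second, Section 11.1 fixes a hypothesis and a test for units, but Section 11.3 does not carry this into the sequence that controls Type I error. On its face, the sentence on tests sends units to Fisher-Freeman-Halton, which is not the test that was powered. For chest tube drainage the categorical comparison is marked as secondary to the t-test: "An additional analysis of 24-hour CTD will compare the frequency of subjects falling into volume categories", with the categories listed. The transfusion sentence has no such label and no unit categories. A confirmatory step should have one measure and one deciding test, named in advance. Otherwise the stated power may not apply to the test that is finally used.

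**Working it through.** **1. Reproduce the stated power (units).** Inputs from Section 11.1: n = 57 evaluable per arm, two-sided alpha 0.05, unequal-variance t-test.

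Formulas: SE = √[(s₁² + s₂²)/n]; noncentrality δ = difference/SE; Satterthwaite df = (s₁² + s₂²)²(n − 1)/(s₁⁴ + s₂⁴); power from the noncentral t distribution.

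| | Difference (units) | SE | δ | df | Power | Stated |
|---|---|---|---|---|---|---|
| Platelets | 1.6 − 0.32 = 1.28 | √[(0.81 + 4.84)/57] = 0.315 | 4.07 | 74.2 | 97.99% | 98.0% |
| PRBC | 4.4 − 1.3 = 3.1 | √[(4.41 + 32.49)/57] = 0.805 | 3.85 | 70.9 | 96.71% | 96.7% |

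Both figures reproduce to the printed decimal. They come from the unit inputs and are correct for units.

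**2. Can the same figures serve for mL?** If every unit had the same volume c, the difference and the SE would both be multiplied by c, and δ and the power would not change. The documents do not say that unit volume is constant, and they give no mean or SD in mL for either product. Power for mL therefore cannot be calculated from them.

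**3. Does it matter which test decides?** The documents give no distribution, so I assume negative binomial counts matched to the Section 11.1 means and SDs, with size r = m²/(SD² − m):

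- platelets: 0.1024/0.49 = 0.21 (treatment) and 2.56/3.24 = 0.79 (control)
- PRBC: 1.69/3.11 = 0.54 (treatment) and 19.36/28.09 = 0.69 (control)

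The first four rows below come from simulated trials with 57 per arm, 1,500 per endpoint. The Fisher-Freeman-Halton p-value was approximated by sampling tables with fixed margins.

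| Deciding test | Platelets | PRBC |
|---|---|---|
| Unequal-variance t-test, units | 99.6% | 99.7% |
| Mann-Whitney, units | 99.8% | 97.9% |
| Fisher-Freeman-Halton, each count its own category | 97% | 68% |
| Same, PRBC repeated in a separate run | – | 63% |
| Fisher-Freeman-Halton, categories 0 / 1 / 2–4 / 5–10 / >10 | – | 94% |

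The two ungrouped PRBC results centre on about 65%. The grouped categories are the PRBC bands of the UDPB table, used for illustration because Section 11.3 defines none for transfusions. The t-test values differ from those in step 1 because the counts here are skewed. Fisher-Freeman-Halton treats the categories as unordered, so it loses power when PRBC counts spread over many sparse values.

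**The case against.** **The measure is already fixed.** Section 11.1 states the hypotheses on mean units, and the steps in the sequence are naturally read as those hypotheses. In Section 11.3 the word *all* can be taken to put t-tests on both measures, with Fisher-Freeman-Halton as an extra. This is the better reading, and it stands. It does not settle the matter: each step would still have two measures and more than one test, none named as deciding, and the variance assumption behind the power is not repeated.

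**Detail belongs in the SAP.** Section 9 says that the analyses are only briefly described in Section 11 and will be detailed there. A SAP could close the second gap, but the supplied text has no such detail on these steps. It would not correct the Synopsis, whose label is wrong as written.

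**Stronger readings that the documents do not support.**

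- *Inflated Type I error.* A reader might infer that any of several tests could be used to declare a step significant. No passage grants that choice.
- *A fallback that is bound to be used and does harm.* The SDs exceed the means, so a reader might infer that the Section 11.1 inputs already trigger the nonparametric replacement. The trigger is not specified, so it cannot be shown to be met, and unequal SDs breach no assumption of an unequal-variance test. In simulation, a switch to Mann-Whitney after a normality check kept Type I error at 4.4–4.9% (negative binomial counts). Mann-Whitney power was 97–100% across the assumed count distributions.
- *Lower power for mL.* Any figure would need an invented model for volume per unit.
- *Chest tube drainage.* It carries the same fallback clause, but its power exceeds 99.9% by either test.

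**Conclusion.** The point holds in two parts of unequal weight.

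1. **Synopsis label: an error in the current text.** The 98.0% and 96.7% are units power, as the recalculation from Section 11.1 confirms. They are attached to mL, for which nothing has been derived. This rests on no assumption beyond the documents.
2. **Section 11.3: incomplete specification.** Mean units by t-test is the likelier intention, but it is not stated where the sequence is defined. The consequence depends on the test. Mann-Whitney on units would cost nothing of note. Fisher-Freeman-Halton would leave PRBC power unassured, at about 65% ungrouped and 94% grouped, against the stated 96.7%. These two values assume negative binomial counts and, for the second, the illustrative categories. They apply only if that test decides, which Section 11.1 argues against.

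The reach is the last two steps of the sequence. The sample size, the primary endpoint and the units power figures stand.

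**What to change.** 1. **Synopsis.** In the power sentence, replace volume in mL with units for both products. In the list of powered secondary endpoints, do not describe mL as powered.
2. **Section 11.3.** State, in the paragraph on tests and in the testing sequence, that each transfusion step is decided by mean total units using the unequal-variance t-test, to match Section 11.1. Label volume in mL and Fisher-Freeman-Halton as supportive.
3. **If a nonparametric replacement is kept for these steps,** name the test and its trigger in advance.

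The change is wording in the Synopsis, Section 11.3 and the SAP, best made before the unblinded interim analysis. It needs no new data and no change in sample size, and the stated power is kept. The one cost is that mL results become explicitly supportive.
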